1.10 Summary

This is an observational study; there is no departure from standard care at any stage. It involves the collection of data that has already been collected for clinical or quality assurance purposes.

In this study we will be collecting information about intravenous fluid intervention (type of fluid and amount) for adult patients undergoing major surgery (duration >2 hours and at least one overnight stay). Data will be collected over a 12-week period. Specifically, the association of these fluids with kidney function will be investigated. Perioperative care and fluid intervention therefore will remain completely at the discretion of the treating clinicians.

The current study will inform clinicians looking after patients undergoing major surgery about the effects of these fluids on renal injury.

This study will be also be used in Fulfilment of University of Melbourne BSc Honours Project for [name].

FLUid intervention and **Renal Outcome Trial** in patients undergoing major surgery: an observational single-centred study (**FLURO TRIAL**). Version 2, 31st Mar 2014

OBJECTIVES

The overall objective of this study is to determine the association between perioperative intravenous fluids and renal function in adult patients undergoing major surgery.

The choice of perioperative intravenous fluid intervention such as Saline (0.9%) vs. Plasmalyte vs. Hartmann's solution will be entirely at the discretion of the all clinicians caring for the patients.

Specifically, we aim to establish the association of Saline (0.9%), Plasmalyte and Hartmann's solution on:

1. The development of acute kidney injury in hospital
2. The development of biochemical and acid-base derangements
3. The development of postoperative complications
4. Requirements for ICU
5. Requirement for dialysis or hemofiltration
6. Duration of ICU stay
7. Hospital length of stay
8. Hospital mortality

STUDY DESIGN

1.11 General

This study is a single-centred prospective observational study on the effects of intravenous fluids on renal function in adult patients undergoing major surgery.

1.13 Inclusion criteria

Patients aged ≥ 18 years admitted to the Austin Hospital who receive major surgery. For the purpose of the study, major surgery will be defined as any surgery longer than 2 hours and requiring a least one night of post-operative hospital stay.

1.14 Exclusion criteria

- Patients who are < 18 years in age
- Patients undergoing liver transplantation (these patients require specific crystalloid solutions as part of the Austin Hospital perioperative fluid intervention protocol).

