1.3 Coordinating Department

Department of Anaesthesia
Austin Hospital
Heidelberg, Victoria
Australia

STUDY SYNOPSIS

Title:	Fluid intervention and Renal Outcome Trial in patients undergoing major surgery: an observational single-centred study (FLURO Trial).
Short Title:	Fluid therapy in major surgery.
Design:	Single-centred, prospective observational study. Information about intravenous fluid intervention (type of fluid and amount) for adult patients undergoing major surgery (duration >2 hours and at least one overnight stay) will be collected over a 6-week period. The effects of these fluids on renal function will be investigated.
Study Centers:	1
Hospital:	Austin Hospital
Study question:	What are the association between perioperative intravenous fluids and renal function in adult patients undergoing major surgery at a University teaching hospital.
Study Objectives:	To determine the association between perioperative intravenous fluids and renal function in adult patients undergoing major surgery.
Primary Outcome:	Acute kidney injury (AKI), defined by an increase in creatinine greater than 25% or 0.5 mg/dL (44 µmol/L) from baseline to peak value within the first 72-hours postoperatively.
Secondary Outcomes:	Serum electrolytes Acid base disturbances Post-operative complications Requirements for ICU Requirement for dialysis or hemofiltration Duration of ICU stay Hospital length of stay In-hospital mortality
Inclusion criteria:	Adult patients ≥ 18 years Elective or emergency surgery Surgery duration > 2 hours Requiring at least one overnight stay
Exclusion criterion:	<18 years in age Liver transplantation
Number of planned Subjects:	400-600

FLUId intervention and **Renal Outcome Trial** in patients undergoing major surgery: an observational single-centred study (**FLURO TRIAL**). Version 2, 31st Mar 2014

Investigational product:	Nil
Safety considerations:	
This is an observational study only. There is no departure from standard care at any stage. It only involves the collection of data that has already been collected for clinical or quality assurance purposes.
 
Perioperative care and fluid intervention will remain completely at the discretion of the treating clinicians.

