1.6 Study design

This study aims to observe the association between perioperative intravenous fluids have and renal function in adult patients undergoing major surgery. **It is a single-centered, prospective observational study and therefore does not change the standard of care in any way.** All patients undergoing surgery at Austin Hospital will be given the perioperative fluids at discretion of the treating clinicians.

The study will be conducted over a 12-week period, allowing a wide variety of amount and type of fluids given to the patients. Austin Hospital staff specialists in anaesthesia agree that on the basis of current evidence, Saline (0.9%), Plasmalyte or Hartmann's solution are equally acceptable for crystalloid fluid therapy in every situation requiring major surgery with the exclusion of surgery for liver transplantation where specific hospital perioperative fluid protocols are used in these settings.

As there is no departure from standard care for this study, Saline (0.9%), Plasmalyte and Hartmann's solution will be available for administration to all patients undergoing major surgery. In the situations, where, in the opinion of the treating anaesthetist or clinician, there is a clinical indication for other types of fluid e.g. colloids, blood, dextrose etc, again there will be no deviation from standard care in any way.

All adult patients who undergo major surgery will be analysed. The primary outcome will be the proportion of patients with kidney injury or failure based on established criteria⁵. Secondary outcomes will include delta creatinine (the difference between baseline and peak creatinine), serum electrolyte levels, acid base disturbances, requirements for ICU, duration of ICU stay, hospital length of stay, complications and in-hospital mortality.

All of the data required for this study are collected routinely as part of standard clinical care and/or quality assurance activities⁶.

FLUid intervention and **Renal Outcome Trial** in patients undergoing major surgery: an observational single-centred study (**FLURO TRIAL**). Version 2, 31st Mar 2014

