1.17.1 General

The primary outcome measure will be acute kidney injury (RIFLE-criteria) defines as AKI, defined as an increase in creatinine greater than 25% or 0.5 mg/dL (44 $\mu\text{mol/L}$) from baseline to peak value within the first 48-hours postoperatively.

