1.26 Analysis plan

A complete description of the statistical analyses will be specified in a statistical analyses plan, finalised prior to completion of the study.

All analyses will be conducted on an intention-to-treat basis.

The primary analyses will be unadjusted analyses in which binary outcomes will be compared using relative risks with 95% confidence intervals and chi square tests and continuous outcomes will be compared with the use of mean differences and unpaired T-tests assuming that normality assumptions are met. If normality assumptions are not met then we plan to attempt simple data transformation, such as a logarithm transformation, and if this fails to proceed to a Mann-Whitney rank based test. Adjusted analyses will be performed using Poisson regression for binary

FLUid intervention and **Renal Outcome Trial** in patients undergoing major surgery: an observational single-centred study (**FLURO TRIAL**). Version 2, 31st Mar 2014

outcomes and linear regression for continuous outcomes. Baseline covariates will include age, gender, elective vs. emergency surgery, surgical specialty of admission, type of operation, and baseline serum creatinine level. Survival times will be compared using log-rank tests and presented as Kaplan-Meier curves. Multivariable models will be developed to study the predictors of AKI and the independent association between fluid choice and renal outcomes.

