1.27 Sub-groups

There will be the following subgroups:

- Patients undergoing abdominal surgery
- Patients undergoing vascular surgery
- Patients undergoing thoracic surgery
- Patients undergoing other surgeries (orthopaedics, urology etc.)
- Patients undergoing emergency surgery

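### Nephrectomy is eligible, and the primary AKI rule makes no allowance for removed kidney tissue, so the operation itself can produce an AKI event whatever fluid was given

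*Protocol*

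**What the plan says.** Section 1.13 defines major surgery as "any surgery longer than 2 hours and requiring a least one night of post-operative hospital stay", with no limit on the organ operated on. Section 1.14 lists two exclusions, age under 18 and "Patients undergoing liver transplantation (these patients require specific crystalloid solutions as part of the Austin Hospital perioperative fluid intervention protocol"). The second is justified by a fluid protocol, not by any effect of the operation on creatinine. Section 1.6 adds: "All adult patients who undergo major surgery will be analysed". Urology is inside the population: section 1.27 gives it as an example within one subgroup, "Patients undergoing other surgeries (orthopaedics, urology etc.)", and the synopsis lists it in the same way. Nephrectomy is not mentioned anywhere.

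Section 1.17.1 has AKI "defined as an increase in creatinine greater than 25% or 0.5 mg/dL" (44 µmol/L) from baseline to the postoperative peak. The window is 48 hours there, while the synopsis has "from baseline to peak value within the first 72-hours postoperatively". Neither place makes an exception for kidney surgery.

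Section 1.26 states: "The primary analyses will be unadjusted analyses". Surgical specialty and type of operation are listed as two separate covariates, but only for the adjusted models.

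**The concern.** Creatinine rises when filtering tissue is removed, and the endpoint cannot tell that rise from kidney injury. A patient who loses a functioning kidney at surgery can meet the primary endpoint with no contribution from fluid. Such events enter the comparison between fluids on the same footing as any other AKI.

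Two things are at stake. If nephrectomies are spread evenly over the fluids, they add the same number of events to each group and pull the relative risk towards 1. If they are not, which is possible because clinicians choose the fluid, they move it in either direction. In both cases the overall AKI rate is inflated. That matters beyond this study, because the rationale section offers its outcome data as input to power calculations for later trials.

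**Working it through.** **Inputs from the protocol.** The AKI threshold is +25% or 44 µmol/L. The window is 48 hours (section 1.17.1) or 72 hours (synopsis). Planning rates are 14% and 8.4% (section 1.25), and the sample is 400 to 600 patients.

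**Inputs assumed.** The protocol gives neither the share of nephrectomies, f, nor the proportion of them meeting the rule whatever the fluid, q. I use f = 2% to 10% (8 patients out of 400 up to 60 out of 600) and q = 50% to 100%. For the kinetics I assume a creatinine distribution volume of 42 L and a starting GFR of 100 mL/min (144 L/day).

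**Step 1: GFR loss needed.** At steady state creatinine is proportional to 1/GFR, so the rise is 1/(1 − loss) − 1. A 25% rise needs a loss of 1 − 1/1.25 = 20%.

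| GFR loss | Steady-state rise | Exceeds 25%? |
|---|---|---|
| 15% | 18% | no |
| 20% | 25% | no (at the limit) |
| 25% | 33% | yes |
| 35% | 54% | yes |
| 50% | 100% | yes |

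The absolute limb adds little at small losses. A rise of 44 µmol/L that is also no more than 25% requires a baseline of at least 44/0.25 = 176 µmol/L.

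**Step 2: is the rise reached inside the window?** With R = 1/(1 − loss), c(t)/c0 = R − (R − 1)·exp(−t/τ), where τ = 42/(144 × (1 − loss)) days. Setting c(t)/c0 = 1.25 gives t = −τ·ln[(R − 1.25)/(R − 1)].

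- Loss 25%: R = 1.333, τ = 9.3 h, t = −9.3 × ln(0.0833/0.3333) = 12.9 h.
- Loss 35%: R = 1.538, τ = 10.8 h, t = −10.8 × ln(0.2885/0.5385) = 6.7 h.
- From a starting GFR of 60 mL/min the times are about 22 h and 11 h.

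All four fall within both stated windows, so the conclusion does not depend on which window is right.

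**Step 3: even spread.** The planning contrast without nephrectomy is 8.4/14 = 0.60. With an equal share f in both groups, each rate becomes p(1 − f) + f·q.

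- f = 2%, q = 50%: 0.14 × 0.98 + 0.01 = 14.7%, and 0.084 × 0.98 + 0.01 = 9.2%. RR = 0.63. Nephrectomies meeting the rule are 8% of all events.
- f = 5%, q = 80%: 17.3% and 12.0%. RR = 0.69, and 27% of events.
- f = 10%, q = 100%: 22.6% and 17.6%. RR = 0.78, and 50% of events.

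**Step 4: uneven spread, no fluid effect.** Take 8.4% AKI in everyone else in both groups, and q = 80%.

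- Shares 5% and 2%: (0.084 × 0.95 + 0.04)/(0.084 × 0.98 + 0.016) = 0.1198/0.0983 = 1.22.
- Same shares reversed: 0.0983/0.1198 = 0.82.

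**The case against.** **The adjusted models may deal with this.** Section 1.26 names type of operation as well as surgical specialty, and plans multivariable models for the independent association of fluid with renal outcomes. If the operation is coded finely enough, much of the confounding could go in those models. This stands for the secondary analyses. It does not change what counts as an event, and it leaves the unadjusted primary result as it is.

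**The size is assumed.** This stands too. The protocol gives no nephrectomy numbers, and with few cases the effect is small. Under an even spread the risk difference also moves little: from 5.6 points to between 5.5 (14.7 − 9.2) and 5.0 (22.6 − 17.6).

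**Fluid choice that varies by surgical list confounds every high-risk operation, not only nephrectomy.** This is true, and leaving out nephrectomy does not cure that wider problem. What is particular to nephrectomy is that the endpoint itself can be produced by the operation.

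**Broad inclusion is deliberate, and analysis detail belongs in the SAP.** The breadth is a fair choice for a preliminary cohort, and the fix keeps it. But the endpoint definition is fixed in this protocol without exception, so the gap is not just detail left for later.

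A reader might go further and infer that almost every nephrectomy will count as AKI. The documents do not support that. Losses of 20% or less, as may occur with partial nephrectomy, do not meet the 25% rule. A reader might also infer that the protocol attributes each such rise to fluid, or treats urology as a subgroup of its own. It does neither: it compares AKI proportions under a stated aim of association, and urology is only an example within the other-surgeries subgroup.

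**Conclusion.** The point holds in a limited form. As written, nephrectomy patients enter the primary analysis, and the AKI rule can be met by the loss of kidney tissue alone once that loss exceeds 20% of GFR. Under the assumed kinetics, losses of 25% to 35% get there well inside 48 hours.

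The consequence is an inflated AKI rate, together with a relative risk that is diluted under an even spread (0.60 to between 0.63 and 0.78) or displaced under an uneven one (1.22 or 0.82 for shares of 5% and 2% with no fluid effect). These figures illustrate the mechanism. They rest on assumed shares and proportions and are not estimates for this hospital. The eligibility rules, the endpoint and the unadjusted primary analysis are stated in the protocol, so the mechanism itself needs no assumption about case numbers. The protocol should be changed, but the point does not by itself invalidate the study.

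**What to change.** Keep nephrectomy patients in the cohort for the non-renal outcomes. In section 1.17.1, and in the synopsis where the definition is repeated, state that patients having a nephrectomy, identified from the operation record, are not evaluable for the AKI outcome and are left out of the primary AKI analysis. Add a sensitivity analysis that includes them, with partial nephrectomy shown separately, because its loss may stay below the threshold.

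The change touches no patient care. It costs slightly fewer patients in the primary analysis, a look at the operation record where surgery is coded only by broad category, and an AKI result that does not apply to nephrectomy.

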Potassium (K ⁺), meq/L	4.0 (3.5 to 5.0)	5	0	0
Calcium (Ca ²⁺), meq/L	2.4 (2.3 to 2.6)	0	0	0
Magnesium (Mg ²⁺), meq/L	2.0 (1.4 to 2.4)	3.0	0	0
Acetate, meq/L	0	27	0	0
Gluconate meq/L	0	23	0	0
Lactate, meq/L	1.0 (0.5 to 2.0)	0	0	0
Strong Ion Difference meq/L	44	49	0	0

*All fluids are manufactured by Baxter Healthcare, Toongabie, NSW.

**Median, Reference Range

FEASIBILITY AT AUSTIN HOSPITAL

The departments of Anaesthesia and Intensive Care at Austin Hospital have completed 6 fluid intervention studies, and currently there is one fluid intervention study still underway in the setting of renal transplantation.

Fluid intervention in liver resection

Recently, the authors completed a multicentre randomized double-blind controlled multicentre study of Plasmalyte vs. Hartmann's solution in patients receiving liver resection³². Participants were randomized to Plasmalyte or Hartmann's solution for intraoperative fluid intervention. Primary outcome: base-excess immediately after surgery. Secondary outcomes: lactate levels, strong-ion-difference (SID), total weak acids, net-unmeasured-ions, changes in liver enzymes, perioperative complications and duration of hospital stay.

Results: 60 participants were recruited from 4 tertiary-level hospitals. Both groups were matched according to baseline characteristics, extent of resection, and surgery duration. There were no differences in the volume of trial fluid used, perioperative fluid balance, or urine output. Plasmalyte was not inferior to Hartmann's for the

FLUid intervention and **Renal Outcome Trial** in patients undergoing major surgery: an observational single-centred study (**FLURO TRIAL**). Version 2, 31st Mar 2014

primary endpoint. Plasmalyte base-excess was 0.8mmol/L greater (95%CI: -0.4 to 2.0;P=0.18). This was associated with hyperchloraemia (Difference 1.7mmol/L, 95%CI: 0.2 to 3.2mmol/L, p=0.03) and hyperlactaemia (Difference 0.8mmol/L, 95%CI: 0.2 to 1.3mmol/L; P=0.01) in the Hartmann's group. In the Hartmann's group 23 patients (77%) had a lactate above the reference range compared to 14 patients (47%) in the Plasmalyte group, P=0.02. Complications were more frequent in the Hartmann's Group (56% vs. 20%, 95%CI: 1.3 to 6.1;P=0.007). Median length of hospital stay: 5.9 days vs. 7.8 days (P=0.041) favouring Plasmalyte group.

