Finally, we tested the hypothesis that a cardiopulmonary bypass prime with lactate would be associated with less acidosis than a prime with only chloride anions because of differences in the measured strong-ion-difference. We randomised 20 patients to a 1500 ml bypass prime with either a chloride-only solution (Ringer's Injection) or a lactated solution (Hartmann's solution). We found that the chloride-only group had greater acidosis with lower base-excess and pH. Contrary to our hypothesis, however, the difference between the groups was not due to a difference in the measured strong-ion-difference. When the difference in standard base-excess between the groups was greatest, the difference in the measured strong-ion-difference was only very small. There was however, a difference in the net-

unmeasured-ions (strong-ion-gap). We concluded that acid-base changes with cardiopulmonary bypass might differ with the prime but that the early differences between chloride-only and lactated primes appear not to be due to differences in the measured strong-ion-difference. We suggested that future studies examine other possible mechanisms including unmeasured ions.

Fluid intervention in renal transplantation

Currently the authors are half way through a randomised trial evaluating the use of either Saline (0.9%) or Hartmann's solution in patients undergoing renal transplantation³⁵. We hypothesised that the balanced crystalloid fluid Plasmalyte, will have more favourable effects on metabolic acidosis and early graft function compared to Saline (0.9%). Adult patients (age > 18 years) undergoing deceased donor renal transplantation (heart-beating or non heart-beating) are included with the primary endpoint being base deficit immediately post surgery in the Post Anaesthesia Care Unit and at 24 & 48 hours postoperatively. A variety of secondary outcomes are being measured including potassium levels, strong-ion-difference, renal biomarkers, requirements for postoperative dialysis, adverse events and hospital stays (days). We have completed recruitment of 20 patients with a total of 50 participants expected. There are no results at this early stage.

The department of anaesthesia and intensive care have an established research infrastructure and have participated in a number of large-scale studies leading to a number of recent NEJM publications³⁶⁻⁴⁰.

CHEST Study and SAFE Studies

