1.15 Baseline data

The following baseline data will be collected:

- Age

FLUid intervention and **Renal Outcome Trial** in patients undergoing major surgery: an observational single-centred study (**FLURO TRIAL**). Version 2, 31st Mar 2014

- Gender
- Admission type (elective vs. emergency)
- Type of surgery (hepatobiliary, colorectal, upper GI, orthopaedic etc.)
- If admitted to ICU: Chronic APACHE co-morbidities (including long-term dialysis)
- If admitted to ICU: APACHE-III admission diagnosis⁴²
- If admitted to ICU: Illness severity based on the on the APACHE-III risk of death score⁴²
- Baseline creatinine.
- Baseline biochemistry

(Note: - all of these data are routinely collected for quality assurance purposes or as measured as part of usual clinical care)

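### Patients on long-term dialysis and those undergoing kidney transplantation are kept in the AKI and dialysis endpoints, which do not measure new kidney injury in them

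*Protocol*

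**What the plan says.** **Who is eligible.** Section 1.13 admits adults having major surgery: "major surgery will be defined as any surgery longer than 2 hours and requiring a least one night of post-operative hospital stay". Section 1.14 removes only people under 18 and "Patients undergoing liver transplantation (these patients require specific crystalloid solutions as part of the Austin Hospital perioperative fluid intervention protocol"). The Study Synopsis gives the same two exclusions, "<18 years in age Liver transplantation". Section 1.6 adds: "All adult patients who undergo major surgery will be analysed".

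**What is counted.** The Synopsis and section 1.17.1 define AKI as a creatinine rise of more than 25% or 44 µmol/L from baseline to peak, with no condition on baseline renal function. (The window is 72 hours in one place and 48 in the other; this point does not depend on which applies.) The Synopsis, the Objectives and section 1.17.2 list a need for dialysis or hemofiltration as a secondary outcome, without limiting it to new treatment.

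**What is recorded.** Section 1.15 lists baseline creatinine and type of surgery for everyone. Dialysis status appears only here: "If admitted to ICU: Chronic APACHE co-morbidities (including long-term dialysis").

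**How it is analysed.** Under section 1.26 the primary analyses are unadjusted. Baseline creatinine and type of operation enter only the adjusted models.

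**The concurrent trial.** Under Feasibility at Austin Hospital, the protocol reports that "currently there is one fluid intervention study still underway in the setting of renal transplantation". It is described as "a randomised trial evaluating the use of either Saline (0.9%) or" another crystalloid, and "Adult patients (age > 18 years) undergoing deceased donor renal transplantation (heart-beating or non heart-beating) are included". Section 1.16 leaves fluid choice in the present study wholly to the treating clinicians.

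**The concern.** The first stated aim is the association of the fluids with the development of AKI in hospital. A patient already on maintenance dialysis has little or no kidney function left to injure, and creatinine moves with the dialysis schedule. A patient receiving a new kidney starts from a high creatinine that falls if the graft works. In both groups the creatinine rule records something other than new injury. A patient who simply continues maintenance dialysis after surgery also meets the dialysis outcome as worded.

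The protocol itself shows that both kinds of patient are foreseeable: it names long-term dialysis as a baseline item, and it describes a kidney-transplant fluid trial in the same departments. With an unadjusted primary comparison, each misclassified patient goes straight into the relative risk. Because dialysis status is not a listed field outside ICU, such patients could not be reliably found and set aside later from the listed data.

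**Working it through.** **1. Where the absolute limb becomes the easier one.** The two limbs are equal when 0.25 × baseline = 44, so baseline = 176 µmol/L. Above that, 44 µmol/L is the smaller rise. At assumed baselines:

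- 500 µmol/L: 44/500 = 8.8%
- 600 µmol/L: 44/600 = 7.3%
- 800 µmol/L: 44/800 = 5.5%

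Rises of that size can occur between dialysis sessions without new injury.

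**2. Design contrast.** Section 1.25 gives 14% and 8.4%, so the relative risk is 0.14/0.084 = 1.67 and the difference is 5.6 percentage points. These are RIFLE injury-and-failure rates from a critically ill cohort. They serve here only as the protocol's own planning contrast. The power claimed in section 1.25 is a separate matter and is not used.

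**3. Equal misclassification in both groups.** Let f be the share of affected patients and q the proportion of them meeting the creatinine rule whatever their fluid. Neither is in the documents. The observed rate is p' = (1 − f)p + f·q.

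| f | q | Rate, 14% group | Rate, 8.4% group | RR | Share of events from affected patients |
|---|---|---|---|---|---|
| 1% | 50% | 0.99 × 0.14 + 0.005 = 0.1436 | 0.99 × 0.084 + 0.005 = 0.0882 | 1.63 | 0.005/0.1159 = 4% |
| 5% | 50% | 0.95 × 0.14 + 0.025 = 0.158 | 0.95 × 0.084 + 0.025 = 0.1048 | 1.51 | 0.025/0.1314 = 19% |

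The last column divides f·q by the mean of the two rates, taking equal groups. Over a wider range (f from 1% to 10%, q from 20% to 80%) the relative risk runs from 1.65 down to 1.32.

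False events and false non-events act differently here. The risk difference shrinks by the factor (1 − f) whatever q is: to 5.54 points at 1% and 5.32 at 5%. The relative risk is diluted only through false events. If q were 0, both rates would shrink by the same factor and the ratio would stay at 1.67.

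**4. Unequal misclassification.** Suppose there is no true effect, with 10% AKI in each group, and affected patients in one group only, with q = 50%.

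- 5% affected: 0.95 × 0.10 + 0.05 × 0.5 = 12% against 10%. RR is 1.20 if they are in the saline group and 10/12 = 0.83 if they are in the comparator.
- 10% affected: 0.90 × 0.10 + 0.10 × 0.5 = 14% against 10%. RR is 1.40 or 10/14 = 0.71.

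Table 1 gives potassium of 5 meq/L in Plasmalyte and 0 in saline, so fluid choice could plausibly follow renal status. The protocol has no data on whether it does.

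**5. Co-enrolment.** Section 1.16 says clinicians choose the fluid. The renal-transplant trial assigns it by randomisation. Both statements cannot hold for a patient in both studies. The trial expects 50 participants and has recruited 20; the documents do not say how many would overlap.

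**The case against.** **The data are not blind to renal status.** Baseline creatinine and type of surgery are recorded for every patient and are prespecified covariates. A kidney-transplant operation should be identifiable, a very high baseline creatinine is visible, and the Lay Summary says data come from medical records, so dialysis status could probably be retrieved. A reader might infer that the plan cannot correct the problem at all; that goes too far. What remains is that the primary analysis is unadjusted, that a covariate does not reclassify a wrong outcome, and that creatinine alone does not separate dialysis from advanced kidney disease without dialysis.

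**The SAP may define analysis sets.** True in general. But eligibility and baseline fields are fixed in the protocol, section 1.6 says all such adults are analysed, and an SAP cannot reliably separate patients whose status is not a listed item.

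**Unbalanced bias is not shown.** Section 1.6 reports that staff regard the three fluids as equally acceptable outside liver transplantation. A reader might infer that false events must favour one fluid. The documents support only the possibility.

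**The liver-transplant parallel is loose.** Liver transplantation is excluded because a hospital fluid protocol governs that surgery. The renal study is a trial of about 50 deceased-donor transplants and does not set fluid for every kidney transplant. The conflict with clinician discretion therefore covers co-enrolled patients only.

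**Not every transplant recipient is affected.** In a patient with an established working graft having other surgery, a creatinine rise is still interpretable.

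**Conclusion.** The point holds for two groups: patients on long-term dialysis and patients undergoing kidney transplantation. Both are eligible and analysed, and in both the AKI rule misclassifies in either direction. For patients on long-term dialysis, the dialysis outcome also counts treatment that predates surgery.

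The size cannot be fixed from the documents. If 1–5% are affected and half meet the rule equally in both groups, the design relative risk of 1.67 falls to about 1.63–1.51. If affected patients cluster under one fluid, the bias can go either way; the unequal scenarios only illustrate that.

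A reader might also set an assumed 1–4% of 400–600 patients (4 to 24) against 11.2% of 400–600 (45 to 67 expected events) and conclude that false events are 9–36% as many as the expected ones. The documents do not support that figure. It needs every affected patient to become an event, and 11.2% is the midpoint of ICU RIFLE rates, not a rate for this endpoint in surgical patients.

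The change should be made because it is cheap and removes a foreseeable error in outcome classification.

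**What to change.** - **Section 1.14 and Synopsis:** exclude from the AKI and dialysis endpoints patients on long-term dialysis before surgery, patients undergoing kidney transplantation, and any patient whose fluid is assigned by a concurrent trial. State that patients with an established graft having other surgery stay in. Amend the sentence in section 1.6 on who is analysed, so that it agrees.
- **Section 1.17.2, Objectives and Synopsis:** restrict the secondary outcome to new dialysis or hemofiltration, meaning treatment in a patient not on dialysis before surgery.
- **Section 1.15:** record preoperative long-term dialysis (yes/no) for every patient, not only ICU admissions.
- **Section 1.16:** reconcile the statement on clinician discretion with possible co-enrolment in the renal-transplant trial.

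The cost is one extra field from the medical record and slightly fewer evaluable patients for these endpoints: at the assumed 1–5%, 4 to 6 patients at the low end and 20 to 30 at the high end, out of 400–600.
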